4.5.2 Effectiveness of the educational strategy “I Prefer Plain Water”

A previous study evaluated the effectiveness of the educational strategy to increase water consumption of first, second, and third graders in Mexico City. For this purpose, a community intervention test was conducted across eight elementary schools in the Coyoacán Delegation during the 2014-2015 school year. A 3-day beverage consumption record (two weekdays and one weekend day) was obtained from all participants. All schools were provided with water bottles inside the classrooms, and the children received a reusable 600-mL bottle. The schools were randomly assigned to an educational intervention group (IG) or a control group (CG). The IG had the educational strategy applied. At the end of the educational session cycle 4 months after baseline, a second record of beverage consumption was obtained, and a third was obtained at the end of the school year (4 months after the second). The strategy was considered effective if the students increased their water consumption by more than 220 mL.

For the analysis, 777 of the 1,105 children included were considered: 413/986 in the IG and 364/762 in the CG with a median age of 7.1 years (range 5.6 to 9.4 years). The children for whom the record of drinks was obtained at all three times were analyzed. From the baseline record to the end (8 months), the IG median increase in water consumption was 167 mL ($P < 0.001$) compared with the CG, which increased 37 mL. The educational strategy was effective for 166/413 of the children in the IG compared with 95/364 of the children in the CG ($P < 0.001$). The IG showed an 80 mL increase in their median total liquid consumption from baseline to first record and a 41 mL increase from the baseline record to the final record. In comparison, the CG increased 33 and 38 mL, respectively. These changes were not significant between the two groups but were significant within the IG from baseline to the first record. Significant differences were found with regard to the consumption of sugary beverages between groups ($P = 0.027$). The IG decreased 42 mL (16.8%), and the CG decreased 36 mL (14.6%) from baseline to the final record. Regarding the consumption of soft drinks, the IG decreased the consumption from 41 mL to 0 mL, whereas the CG reduced from 83 to 33 mL from baseline to the final record ($P < 0.001$). Figure 1 shows the change in beverage consumption in the groups at all three times.

After water, dairy drinks were consumed most often, with a similar median for both groups throughout the trial (i.e., no significant differences). The consumption of hot drinks, soft drinks, and functional beverages was low and did not significantly change throughout the trial.

Figure 1. Change in beverage consumption, Intervention Group (IG) vs Control Group (CG)

* Friedman related samples

The “I Prefer Plain Water” educational strategy effectively increased the consumption of water and reduced the consumption of sugary beverages and soft drinks when evaluated over the short term (4 months after its implementation); however, its long-term effectiveness (1 year later) has not been established.

According to the transtheoric model that uses the stages of change to integrate the processes and principles of change through the main theories of intervention, the maintenance stage in which the change in behavior persists occurs when the behavior is maintained for 6 months or more (17). Based on this idea, the effectiveness of this educational strategy will be evaluated 1 year after the intervention.

5.0 DESCRIPTION OF THE PROBLEM

Obesity prevention in young children should be considered a matter of the highest priority because it is necessary to promote healthy lifestyle behaviors that include (among others) an increased consumption of water and a decreased consumption of sugary drinks.

Studies have shown that school-based interventions affect obesity prevention. To date, educational strategies that promote adequate water consumption have been proposed as short-term strategies. Evidence exists of the need to reinforce these programs so that children continue with their acquired habits.

The educational strategy "I prefer plain water" favorably modifies water consumption when evaluated in the short-term; however, whether this observed change is maintained throughout early elementary education, a period that education specialists have established as essential to sustain healthy habits throughout life, is unknown.

6.0 JUSTIFICATION

The Mexican government identified the promotion of water consumption as a major strategy to reduce the energy density of the diet and thereby help prevent the problems of overweight, obesity, and other diseases associated with the excessive intake of sugary beverages. Thus, the National Agreement for Nutritional Health (ANSA) considers increasing the intake of water and discouraging the consumption of sugary beverages as a priority with regard to the population.

The educational strategy "I Prefer Plain Water" favorably affected water consumption and decreased the consumption of sugary beverages and soft drinks among early elementary school children in Mexico City when evaluated over the short term. The study of its long-term effectiveness is necessary to establish public health policies that maintain healthy lifestyles over time to enhance the quality of life of the population.

7.0 GENERAL OBJECTIVES

This proposal seeks to evaluate the effectiveness of the number of educational strategy interventions to increase the percentage of water consumed among early elementary school students over a 1-year follow-up period.

7.1 Primary Objective

This study seeks to compare the percentage of water consumed among early elementary school children receiving one, two, or three interventions of the educational strategy "I Prefer Plain Water" at a 1-year follow-up evaluation.

7.2 Secondary Objective

This study seeks to compare the monthly water consumption of participating schools during the follow-up period.

This study seeks to describe the annual body mass index (BMI) of the participating students during the follow-up period.

8.0 HYPOTHESES

The percentage of water consumed will be greater in the group of children who will receive all three interventions.

9.0 STUDY DESIGN

Experimental, analytical, longitudinal, and prospective designs will be employed. The assignment will be conducted by each school.

Community Intervention Test

10.0 POPULATION

10.1 Target Population

Children who attend elementary public schools of the Coyoacán Delegation are the target population.

10.2 Eligible Population

First graders attending public elementary schools under the epidemiological surveillance of the Ajusco and Santa Úrsula Health Centers will be recruited during the 2017-2018 school year.

11.0 SELECTION CRITERIA

11.1 Inclusion Criteria

- Healthy children (according to the investigator)
- Both girls and boys
- Children whose parents agree to participation in the study through verbal informed consent
- Children whose parents sign a privacy notice

11.2 Exclusion Criteria

- Children who present with any pathology that interferes with the free consumption of water or with the proper execution of the study
- Children for whom it is not possible to obtain a baseline record of beverage consumption

11.3 Elimination Criteria

- Children who do not attend more than two educational sessions within each grade level
- Children with incomplete or improperly completed beverage records

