12.4 Intervention

At all participating schools, the principal investigator will conduct an approximately 1-hour briefing for parents to 1) explain the study's operational generalities and answer all questions and 2) provide instructions for completing the beverage consumption survey. Subsequently, the 3-day baseline record of beverage consumption will be collected.

At the beginning of the school year, first grade teachers will be trained by a nutritionist (one per school) to dispense the educational sessions (Appendix VI, VII, VIII), and the manual and materials for both teachers and students will be delivered.

The students will receive four educational sessions of approximately 1 hour. These sessions will be given every 2 weeks, and some will be supervised by a nutritionist.

The four schools will be assigned to one of the following three groups based on school enrollment and the interest of the teachers in participating:

Students in Group I will receive the education strategy only during the first grade; students in Group II will receive the educational strategy during first and second grades; and students in Group III will receive the educational strategy during first, second, and third grades.

	1st grade	2nd grade	3rd grade
Group I	X		
Group II	X	X	
Group III	X	X	X

With the delivery of the first educational session, free access to water will be initiated through Welltek water dispensers, model WT-POU-300 A (approved and certified by Cofepris and the National Institute of Physical Educational Infrastructure; INIFED), installed inside the classrooms. Children will also receive a reusable 600-mL bottle (twice) so that they may consume water throughout the day. The availability of water will be guaranteed during four school cycles.

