12.5 Evaluation Process

In September 2017, the medical examination of the students and the process of inclusion will be performed; instructions will be sent to parents, and teacher training will be conducted. During October 2017, the baseline record regarding the consumption of beverages will be collected (Time 1). The educational sessions will be given from November 2017 to January 2018. A second record (Time 2) will be obtained at the end of the interventions in each group (end of June), and a third record (Time 3) will be obtained from each group 1 year after completing the interventions (end of June).

Baseline		End of 1st grade	End of 2nd grade	End of 3rd grade	End of 4th grade
Group I	X	X	X		
Group II	X	X		X	
Group III	X	X			X

 Evaluation 1 year after completing the number of interventions associated with each group

In addition to measurements at baseline and at each evaluation time, body weight will be measured, and lean mass, fat free mass, fat percentage, total body water, and BMI will be analyzed using a body composition analyzer via electrical bioimpedance (TANITA TBF-310 GS). Height will be measured using a portable stadiometer (dry mark, model 213, Hambur Germany). Participants will be measured in light clothing (T-shirt and sport shorts) and without shoes. A nutritionist will be calibrated to perform the measurements. BMI will be classified using the WHO values standardized by age and gender.

The following table summarizes the procedures to be performed throughout the trial.

Procedure	Sep 2017	Jun 2018	Sep 2018	Jun 2019	Sep 2019	Jun 2020	Sep 2020	Jun 2021
School medical examination	X							
Weight, size, and body composition measurements	X	X		X		X		X
Instructions for completing the daily beverage record	X	X		X		X		X
Teacher training	X		X		X			
Daily beverage record	X	X		X		X		X
Group I intervention	X							
Group II Intervention	X							
Group III Intervention	X							

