13.0 SAMPLE SIZE

Considering the results of the previous study where a mean difference of 80.74 mL was found with regard to water consumption with an SD of 399 mL as well as considering an α of 0.05 and a β of 0.1, we used the following formula to calculate a significant difference in means

$$n = [(Z_{1-\alpha} + Z_{1-\beta})^2 * s^2] / d^2$$
$$[(1.96 + 1.28)^2 * 399^2] / 80.74^2 = 256.36$$

N = 257 children

The sample should include 329 first graders (allowing for a 28% loss margin) who will attend the 2017-2018 school year. This sample represents all of the four intervention schools that participated in the previous study.

2016-2017 school enrollment of the intervention schools participating in the previous study

School	Health Center	First grade	Total	Second grade	Total	Third grade	Total	Total school enrollment
Ramón Durand	Ajusco	32 32	64	31 32	63	26 27	53	341
Xitle	Ajusco	27 29 25	81	28 27 29	84	31 30 29	90	529
Guillén de Lampart	Santa Úrsula	28 26 27	81	31 32 30	93	27 27	54	475
Tlamatini	Santa Úrsula	34 35 34	103	36 37 36	101	33 33 33	99	600
			329		278		243	1,604

	Group I	Xitle	81
	Group II	Guillén de Lampart	81
	Group III	Ramón Durand Tlamatini	167

Based on the school enrollment of the current school year (2016-2017), schools with the same number of first graders will be assigned to Groups I and II. For Group III, the schools with the highest and lowest enrollments will be added.

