15.0 STATISTICAL ANALYSIS

The analysis will be performed using the IBM SPSS version 22.0, and non-parametric statistics will be used.

Baseline measurement of beverage consumption (Time 1). The basal consumption of the different beverage categories will be summarized using medians, minimums, and maximums. We will apply the Kruskal-Wallis test (K of independent samples) to compare the differences in baseline beverage consumption among the three groups.

Baseline measurement and at the end of the interventions (Times 1 and 3). The percentage of water consumed at baseline will be compared with that 1 year after finishing the intervention for each group using the Wilcoxon test.

Comparison among the three groups. The percentage of water consumed will be compared among the three groups 1 year after the intervention is completed using Friedman's test of related samples.

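### The attendance elimination rule is applied once in Group I, twice in Group II and three times in Group III, so the analysed groups are selected differently and the comparison can be biased

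*Combined protocol and SAP*

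**What the plan says.** Section 11.3 (Elimination Criteria) removes "Children who do not attend more than two educational sessions within each grade level". A second criterion in the same section removes children with incomplete or badly completed beverage records.

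Section 12.4 (Intervention) sets the number of sessions, "The students will receive four educational sessions of approximately 1 hour", and the grades in which they are given. "Students in Group I will receive the education strategy only during the first grade"; Group II has them in first and second grade; and "students in Group III will receive the educational strategy during first, second, and third grades".

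The primary objective (Section 7.1) compares children "receiving one, two, or three interventions of the educational strategy". The corresponding analysis in Section 15.0 reads "The percentage of water consumed will be compared among the three groups 1 year after the intervention is completed". That section defines no analysis set, does not say what happens to eliminated children and plans no sensitivity analysis. Under Section 12.5, "a third record (Time 3) will be obtained from each group 1 year after completing the interventions", which falls at the end of second, third or fourth grade.

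Section 13.0 has one loss allowance for all groups: 257 children are needed and 329 are to be enrolled, split 81, 81 and 167 across Groups I, II and III.

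**The concern.** Elimination happens after assignment, depends on behaviour during the intervention, and offers more chances of removal to the groups assigned more interventions. By Time 3, Group I has passed one attendance filter and Group III has passed three. If attendance goes with a stable trait that also raises the share of water in a child's intake, such as an engaged family, the retained Group III children are the most selected. They would then show a higher percentage of water even if extra interventions did nothing. Section 8.0 predicts exactly that result.

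If attendance is unrelated to intake, the comparison is not biased, but children with usable Time 1 and Time 3 records are still discarded, mostly from Groups II and III. Those losses draw on the allowance in Section 13.0, which must also cover incomplete records and children who leave.

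The threshold is unclear as well. The sentence can mean that a child attended two or fewer of the four sessions, or that a child missed more than two. It can also be read as requiring failure in every grade rather than in any one. A rule that decides who enters the primary comparison should not be left to interpretation after the data are seen.

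**Working it through.** **The plan's own figure.** Section 13.0 uses a difference of 80.74 mL, an SD of 399 mL, and z values of 1.96 and 1.28:

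n = (1.96 + 1.28)² × 399² / 80.74² = 256.36, rounded up to 257.

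The enrolment target follows as 257 × 1.28 = 328.96, or 329. The allowance for all losses is 329 − 257 = 72 children.

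**Chances to be eliminated.** From Sections 11.3 and 12.4, k = 1, 2 and 3 grades with sessions in Groups I, II and III. With a yearly pass rate p and independent years, the share kept is pᵏ. At p = 0.90 this is 0.90, 0.81 and 0.73.

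**Allowing for children who attend consistently.** The documents give no attendance data, so the following are assumptions:

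- yearly pass rate p of 0.85 to 0.95;
- year-to-year correlation ρ of 0.3 to 0.5;
- correlation r of 0.2 to 0.3 between the attendance trait and the outcome.

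For each child, let M be a standard normal trait. Attendance in a year is √ρ·M + √(1−ρ)·noise, and the child passes if this exceeds the (1−p) normal quantile. The outcome correlates r with M, and no group effect is present. A simulation of 4,000,000 children gives:

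| p | Share kept, I / II / III | Kept of 81 / 81 / 167 | Lost of 329 | III minus I with no true effect |
|---|---|---|---|---|
| 0.95 | 95 / 91 / 87–88% | 77 / 73–74 / 145–147 | 31–33 | 0.019–0.030 SD |
| 0.90 | 90 / 82–83 / 76–78% | 73 / 67 / 127–131 | 58–63 | 0.032–0.048 SD |
| 0.85 | 85 / 74–76 / 66–69% | 69 / 60–61 / 110–116 | 83–90 | 0.042–0.064 SD |

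The difference is in SD units because the primary outcome is a percentage for which the plan states no SD.

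**Scale.** Ignoring clustering, the standard error of III minus I is √(1/81 + 1/167) = 0.135 SD. The bias lies below it throughout.

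**Other readings of the threshold.** Assume each session is attended with probability 0.90, independently.

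- Kept if at least 3 of 4 attended: p = 0.9⁴ + 4 × 0.9³ × 0.1 = 0.948. The bias is 0.020–0.031 SD.
- Kept unless more than two missed: p = 0.948 + 6 × 0.9² × 0.1² = 0.9963. Retention is 99.6 / 99.3 / 98.9%, about 3 children are lost, and the bias is 0.002–0.004 SD.

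**Other reading of the grades.** If a child is eliminated only for failing in every grade, the order reverses. With independent years and p = 0.90, the shares kept are 1 − 0.1ᵏ = 90 / 99 / 99.9%. Over p from 0.85 to 0.95, with the correlations above, III minus I is −0.011 to −0.041 SD.

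**The case against.** The best case for leaving the rule as a minor matter has five parts.

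- **The text fixes neither size nor sign.** If the rule means missing more than two sessions, about 3 children are lost and the bias is negligible; on the every-grade reading the sign flips. This is true. It limits what can be said about magnitude, but it also shows why the rule cannot stand as written.
- **The bias is small and every driver is assumed.** It is below a standard error that already ignores clustering. At an assumed intraclass correlation of 0.02 to 0.05, with one school each in Groups I and II and two in Group III, that standard error rises to about 0.22 to 0.31 SD. Attendance may mostly reflect ordinary school absence. All of this stands: the rule would not by itself produce a significant result.
- **A stable trait is also present at baseline.** It would largely cancel in the within-group Time 1 to Time 3 Wilcoxon tests and in the effectiveness variable of Section 14.0, which is relative to baseline. That is correct for those analyses. The between-group comparison of Time 3 values has no baseline adjustment and remains exposed.
- **The losses are overstated.** Only at p = 0.85 does the rule alone exceed 72. Some children who fail on attendance would have no Time 3 record anyway. Groups II and III also hold 248 of 329 children (75%), so most losses would fall there under any rule. The first two points stand as limits on the counts. On the third, at p = 0.90 Group I loses 81 − 73 = 8 of the 58–63, about 13–14%, although it holds 25% of the children, so the loss is still unequal.
- **The question is about interventions received.** An attendance condition fits the wording of Section 7.1. However, schools are what is assigned, and Section 3.0 gives the purpose as informing policy on how many interventions to offer. Even an analysis of interventions received should not filter the groups unequally without saying so.

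**Conclusion.** The concern holds. Sections 11.3 and 12.4 together apply the attendance filter once, twice and three times, and nothing in Sections 13.0 or 15.0 offsets this in the Time 3 comparison.

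On the natural reading (two or fewer sessions attended in any grade), the spurious advantage to Group III is about 0.02 to 0.06 SD, and 31 to 90 of the 329 children are removed. Both ranges rest on assumed pass rates and correlations. The bias requires that attendance and share of water are related; without that link, the cost is lost data only. The other threshold reading makes the effect trivial, and the every-grade reading reverses it.

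This should be corrected because it is avoidable and touches the primary comparison, although it is not large enough to decide the trial's result alone. Confidence in the size is moderate at best; the unequal count on the natural reading follows directly from the text.

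**What to change.** In Section 11.3, remove attendance as a reason for elimination from the primary analysis. In Section 15.0, define the primary set as every included child with usable Time 1 and Time 3 records, analysed in the group to which the school was assigned, whatever the attendance.

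Keep an attendance-restricted analysis as a sensitivity analysis. Write its threshold as a count, for example at least 3 of 4 sessions attended, and apply it to first-grade attendance in all groups. First grade is the only grade in which all three groups receive sessions, so the filter is then equal. Report the number of children below the threshold by group and grade.

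The cost is wording in two sections, with no new data. The estimate will include children who received fewer sessions and may be slightly smaller. The change does not remove selection from longer follow-up, since Time 3 comes one and two years later in Groups II and III than in Group I. Nor does it address the assignment of schools by enrolment and teacher interest.

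### Section 11.3 removes the whole child for faulty beverage records and section 15 has no missing-data method, although Time 3 falls about 20, 32 and 44 months after baseline in Groups I, II and III

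*Combined protocol and SAP*

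**What the plan says.** Section 11.3 (Elimination Criteria) has two rules, both acting on the child. One removes "Children with incomplete or improperly completed beverage records". The other removes "Children who do not attend more than two educational sessions within each grade level". Children with no obtainable baseline record are already excluded under section 11.2, so the record rule in 11.3 acts mainly after enrolment.

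Section 12.5 puts baseline in October 2017. The later mark for each group in its table is the "Evaluation 1 year after completing the number of interventions associated with each group": end of 2nd grade for Group I, 3rd grade for Group II and 4th grade for Group III.

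Section 7.1 makes the comparison of one, two and three interventions the primary objective, and section 8.0 predicts its direction: "The percentage of water consumed will be greater in the group of children who will receive all three interventions".

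Section 15 names the Kruskal-Wallis, Wilcoxon and Friedman tests. It defines no analysis population, missing-data method, comparison of retained with eliminated children, or sensitivity analysis. Section 13 allows one overall loss of 28%, not split by group. Section 12.6 plans focus groups to make the journal easier to complete.

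The previous study, described in section 4.5.2, also analysed complete records only: "The children for whom the record of drinks was obtained at all three times were analyzed".

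**The concern.** Two things are at stake.

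The first is information. A rule that removes the child rather than the faulty record throws away valid measurements, including valid Time 3 outcomes.

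The second is comparability. The groups reach Time 3 after very different lengths of follow-up. If children drop out or hand in poor journals at a steady rate over time, the analysed part of Group III is the smallest share of those enrolled. If families who keep returning usable journals also differ in how much water their children drink, the groups compared at Time 3 are selected to different degrees, and part of any Group III advantage could come from that selection. The plan has no analysis that would reveal or limit this.

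The within-group Wilcoxon comparison is less exposed, because it pairs each child with himself or herself. The problem lies mainly in the between-group comparison and in whom the results represent.

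**Working it through.** **The plan's own loss figure.** Section 13 needs 257 children and recruits 329. This reproduces as 257 × 1.28 = 328.96. A 28% loss from 329 leaves 329 × 0.72 = 237, below 257; dividing instead gives 257 / 0.72 = 357. For comparison, section 4.5.2 reports 777 of 1,105 children analysed, a loss of 328 / 1,105 = 29.7% over 8 months.

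**Follow-up to Time 3**, counted from October 2017 (section 12.5):
- Group I, June 2019: 20 months
- Group II, June 2020: 32 months
- Group III, June 2021: 44 months

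The procedures table shows the baseline record under September 2017. Using that month adds one month to every group and leaves the differences of 12 and 24 months unchanged.

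**Retention.** The documents give no loss by group or by time, so a constant annual loss *a* is assumed: R = (1 − a)^(months/12).

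| Assumed annual loss | Group I | Group II | Group III |
|---|---|---|---|
| 10% | 0.90^(20/12) = 0.839 | 0.90^(32/12) = 0.755 | 0.90^(44/12) = 0.680 |
| 15% | 0.85^(20/12) = 0.763 | 0.85^(32/12) = 0.648 | 0.85^(44/12) = 0.551 |

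With the section 13 enrolments of 81, 81 and 167, these leave about 68, 61 and 113 children at 10%, and 62, 53 and 92 at 15%.

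**Spurious difference.** Suppose lost children have a water percentage *g* points below retained ones, with the same *g* in every group (an assumption). The retained mean then exceeds the full-group mean by g × (1 − R). With no true effect, Group III minus Group I is g × (R_I − R_III).

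| Gap g (assumed) | 10% a year: 0.839 − 0.680 = 0.159 | 15% a year: 0.763 − 0.551 = 0.212 |
|---|---|---|
| 0 points | 0 | 0 |
| 5 points | 0.8 | 1.1 |
| 10 points | 1.6 | 2.1 |

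These figures cover all attrition. A child who supplies no Time 3 record has no primary outcome under any rule. Section 11.3 adds only the children who have a usable, or partly usable, Time 3 record and are removed anyway. The documents give no way to count them.

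**How many records each child must supply.** The group table in section 12.5 marks three records for every group: baseline, end of 1st grade and Time 3. The procedures table lists a record every June to 2021 without naming groups. If each group is recorded until its own Time 3, Group I needs 3 records, Group II 4 and Group III 5. The text also places Time 2 at the end of each group's interventions, whereas the group table marks end of 1st grade for all. On either reading there is an intermediate record that can remove a child whose Time 3 record is valid.

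**Attendance rule.** It applies within each grade level, so a child can be removed at one point in Group I, two in Group II and three in Group III. This rule does multiply with the number of interventions.

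**The case against.** The strongest reply is that unequal removal is not shown. On the group table every group must supply the same three records. If loss comes from failing to complete a journal rather than from elapsed time, retention could be similar in all groups, R_I − R_III would be near zero, and so would the bias. That stands: the concern about unequal depletion is conditional on loss growing with time.

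A reader might also infer that the analysed groups are selected toward engaged families in a way that favours the hypothesis. The documents do not support this as fact. They contain no data linking journal completion to water intake; with a gap of zero there is no bias, and with a gap of the opposite sign it would run against Group III.

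It is tempting to compound the previous study's 8-month loss out to 44 months. That should not be done. Its 70.3% is the share of children with all three records, not a rate of loss per month. The denominators in section 4.5.2 also conflict: the arms are given as 986 and 762, which sum to 1,748, not 1,105.

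Reading the rule as covering any faulty record, including an intermediate one, rests on the plural wording and on the previous study's practice. Section 11.3 does not spell it out.

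Finally, excluding badly completed journals is partly legitimate quality control, the focus groups may reduce loss, and the 28% margin shows that loss was foreseen. None of these says how lost children are handled in the analysis or whether they differ from those retained.

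**Conclusion.** The point holds in a limited form. What the documents establish is that section 11.3 removes the child rather than the record, that Time 3 comes about 20, 32 and 44 months after baseline, and that section 15 has no missing-data method and no retained-versus-lost comparison. Whichever way any bias runs, usable outcome data are discarded.

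Bias in the between-group comparison rests on two assumptions: loss grows with time, and completion is related to intake. At 10% to 15% annual loss and a gap of 0 to 10 points, the spurious Group III minus Group I difference from all attrition ranges from 0 to about 2 percentage points. This should not be read as the effect of section 11.3 alone, nor as evidence that bias in favour of Group III will occur. The change should be made: it is cheap, and the plan as written could not detect the problem.

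**What to change.** 1. Do not use the incomplete-records criterion in 11.3 to remove children from the primary analysis. Include every child with a baseline record, and set aside only the invalid record or day.
2. Section 12.6 defines a record as two weekdays and one weekend day, and the dispensers are in classrooms. Where fewer than three days are valid, account for day type when computing the percentage; a plain average of the remaining days can shift it.
3. Analyse all available records in a model with group, time and baseline percentage, with the contrast at each group's own Time 3 as the primary comparison. A child with no post-baseline record stays in the analysis population and the retention table but adds nothing to that contrast.
4. Keep the complete-record set as a sensitivity analysis.
5. Tabulate retention, and baseline percentage for retained and lost children, by group.
6. Treat the attendance criterion in 11.3 the same way: not a ground for removal from the primary analysis, but available for a sensitivity analysis.
7. Reconcile the two tables and the text of section 12.5 on which groups give a record each June and when Time 2 falls.

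The cost is revised wording and modest extra analysis; no new data collection is needed beyond the records already scheduled. The downside is that the model assumes data are missing at random. That is weaker than the missing-completely-at-random assumption behind deletion, but it does not remove bias from unmeasured family engagement. Nor does it address the non-random assignment of schools. Conclusions about Group III should be worded with that caution.
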